- e Visit AOC1D1 shall occur no longer than 6 wks after confirmed disease progression on monotherapy in Arm 2 or 3.

Clinical Trial Protocol BNT111-01

Page 24 of 133 Version: 7.0 Date: 09 FEB 2023

- f "n" represents the number of the respective cycle (e.g., AOC3 means the third cycle of add-on therapy).
- g Visit X should occur 21 (± 3) d after the first day (i.e., treatment visit) of the previous cycle.
- h Continued record of concomitant medication and therapy after add-on, includes any therapies (e.g., prescription drugs, over-the-counter drugs, vaccines, herbal or homeopathic remedies, nutritional supplements) used by a patient in addition to protocol-mandated trial treatment until the SFU2 visit.
- i If baseline and AOC1D1 are on the same day, assessment only needs to be taken once.
- Vital signs (body temperature, pulse rate, respiratory rate, and blood pressure) should be measured prior to the administration of the trial treatments, and at 30 (±10) min, 60 (±10) min, 4 h (±10 min), and 6 h (±10 min) after administration, or if clinically indicated (see Section 8.2.3 for guidelines on reduction or expansion of these time points).
- k At baseline and at EoT assessments must include a full physical examination. Record abnormalities observed on the respective eCRF pages as appropriate. For all subsequent physical examinations perform a limited, symptom-directed examination at specified time points and as clinically indicated at other time points. Record new or worsened clinically significant abnormalities on the AE eCRF.
- I Single 12-lead ECG recordings will be obtained during baseline, at EoT, and as clinically indicated at other time points. Patients should be resting in a supine position for at least 10 min prior to ECG recording. The interpretation of the ECG recording will be done locally by the investigator.
- m Baseline image may not be older than 21 d prior to AOC1D1. Target lesions and non-target lesions can be redefined at baseline assessment for add-on therapy.

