- to screening/baseline (Arms 1 and 2 and add-on treatment). The endpoint is clarified as:
 - Occurrence of expansion of pre-existing or de novo induction of T cells specific for BNT111-encoded antigens at pre-specified time points compared to screening/baseline (categorical ex vivo ELISpot data) (Arm 1 and Arm 2 and add-on treatment)
- · BNT111 target antigen expression, potentially outcomepredictive biomarkers, immune signature molecules (e.g., PD-L1 expression), and potentially prognostic factors in archival tumor tissue at screening and pharmacodynamics markers (e.g., cytokine levels) under treatment. Patients in selected trial sites: tumor infiltrating lymphocytes (TIL) and T-cell receptor (TCR) repertoire characterization at screening/baseline and under treatment. Cytotoxicity assays with autologous tumor cell lines and T cells.

These endpoints are split into the following endpoints.

- Occurrence of BNT111 target Tumor-associated antigen (TAA) expression in tumor tissue at baseline [Positive/Negative] (4 targets).
- Tumor mutational burden (TMB) at baseline [absolute values].
- Other potentially outcome predictive biomarkers. [1]
- Continuous Programmed Cell Death Ligand 1 (PD-L1) Tumor Proportion score (TPS) at baseline in percentage.
- Categorical PD-L1 expression (Positive/TPS≥1% vs Negative/TPS<1%) at baseline.
- Other immune signature molecules. [1]
- Peripheral cytokine profiles under treatment over time [absolute values].
- B-Raf proto-oncogene (BRAF) mutations at baseline.
- Other potentially prognostic factors in archival tumor tissue at screening and pharmacodynamics markers under treatment [1]

Statistical Analysis Plan (SAP) BNT111-01

Page 15 of 78 Version: Final v7.0 Date: 05Mar2024

Objectives	Endpoints
	 Tumor infiltrating lymphocytes (TIL) and T-cell receptor (TCR) repertoire characterization at screening/baseline and under treatment. [1] Cytotoxicity assays with autologous tumor cell and T cells [1]

^{*} Baseline in the main trial (Arm 1) encompasses all data collected before start of trial therapy on Visit C1D1.

^[1] endpoint will be done separately in a biomarker analysis report, which will not be a part of this SAP.

Page 16 of 78 Version: Final v7.0 Date: 05Mar2024

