The Safety set will be used for all safety analyses. The Add-on Treatment set will be used for analysis of both safety and efficacy data. Patients randomized to monotherapy (arm 2 and arm 3) who enter add-on treatment period are included in the analysis using both the mITT set, ITT set and the Add-on Treatment set, unless specified otherwise.

The following will occur for the analysis of ORR, DCR, DOR, TTR, PFS, OS, DEoR and EORTC endpoints and for the exploratory analysis of Duration of Disease Control (DDC):

- Tumor response endpoints ORR, DCR, DOR, DDC, TTR, DEoR and PFS: for the analysis using the set or set (sensitivity analysis for ORR (including DCR)), only the data until the day before first dose of add-on treatment will be used. For the analysis using the Add-on Treatment set, only the data from date of first dose of add-on treatment will be used.
- OS: for analysis using the set and Add-on Treatment set, all data would be used. For the exploratory analysis using the Add-on Treatment set (BNT111 + add-on cemiplimab and cemiplimab + add-on BNT111 treatment groups) the data from first day of add-on treatment would be used.
- For EORTC endpoints (Section 8.4.2.8) the summaries/analyzes will be performed as follows:
 - (i) While using set, data until the day before first dose of add-on treatment would be used.
 - (ii) In addition, a separate summary from first dose of add-on treatment to EOS, for the Add-on Treatment set.

All safety analyses will be based on the treatment actually received by the patient ('as treated'). All other analyses will be based on the treatment the patient was randomized to ('as randomized'), unless stated otherwise.

The following will occur for the analysis of safety data (apart from Adverse events)

- For the analysis of safety data using the Safety set, only data until the day before first dose of add-on treatment, if there is add-on treatment, or all data if there is no add-on treatment will be used.
- For the analysis of safety data using the Add-on Treatment set, only data from date of first dose of add-on treatment will be used.

The primary analysis of the trial will be performed based on all available data from a clinical data cut-off that will occur when all patients are randomized and response evaluable (i.e., having at least 3 post-baseline tumor assessments or discontinued before).

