An analysis update will be performed when the last patient discontinued from the trial and once all patients have been randomized and have been followed-up for at least 24 months. An analysis update may be subsequently performed.

Statistical Analysis Plan (SAP) BNT111-01

Page 30 of 78 Version: Final v7.0 Date: 05Mar2024

Data up to and including the clinical cut-off date will be taken into account for the statistical analysis.

All analyses will be conducted using SAS® version 9.4 or higher.

Baseline is defined as last non-missing value prior to the first dose of trial treatment at C1D1. Assessments performed at C1D1 will be considered for baseline value, unless there is evidence the assessment was performed after trial treatment had been administered. For the add-on treatment if the baseline visit and AOC1D1 are on the same day, the assessment only needs to be taken once. In this case the AOC1D1 would be considered as the baseline value, unless there was evidence that the assessment was done after treatment had been administered.

To identify the baseline value, generally, if there are multiple assessments available for a particular day, the assessment that is closest to the day (and time if collected) of the first dose of the trial treatment (i.e., BNT111 or cemiplimab) will be used as the baseline value in the summary/analyses.

Multiple values at post-baseline visits: if there are multiple post-baseline assessments available within a visit/day, the first value and corresponding date/time will be considered.

Change from baseline will be calculated as follows:

Change from baseline = post-baseline assessment value – baseline assessment value.

If either the baseline or post-baseline assessment value is missing, the change from baseline is set to missing as well.

Duration (Other than "trial treatment duration" defined in Section 8.5.1) will be calculated as follows:

Duration = last observation date - first observation date + 1

For conversion of days to months or years the following rules will be applied:

- 1 month = 30.4375 days
- 1 year = 365.25 days

Trial Day and Treatment Day are defined as follows:

- Trial day:
 - If assessment date < randomization date then trial day = assessment date randomization date
 - If assessment date >= randomization date then trial day = assessment date randomization date + 1
- Treatment Day = treatment date date of first dose +1

That is, trial day 1 indicates the date of treatment initiation.

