8.4 Efficacy analyses

8.4.1 Primary analysis

The primary analyses will be performed using the CCI set.

Definition of primary endpoint

Overall Response Rate (ORR) defined as the proportion of patients in whom a CR or PR is observed as best overall response by blinded independent central review (BICR).

The BICR will provide a response for each patient assessment using the RECIST[©] 1.1 guidelines.

Main analytical approach

The primary statistical objective is to demonstrate that the ORR of BNT111+cemiplimab is greater than CCI using an overall significance level of CCI using an overall significance level of

[figure not shown]
The following null and alternative hypothesis are defined:

[figure not shown]
Statistical Analysis Plan (SAP) BNT111-01

Page 37 of 78 Version: Final v7.0 Date: 05Mar2024

The best overall response for a patient is defined as the best response across all responses prior to the start of new anti-cancer therapy for that patient. It is noted that a tumor response of SD can be confirmed from 36 days after first dose of study drug as the tumor assessment at week 6 (day 42) can be performed in a +/- 1 week window.

[figure not shown]
Statistical analysis

Additionally, a swimmer plot for duration on treatment and overall response assessments based on RECIST for BICR assessment will be presented based on set, add-on treatment set and combination of both (show both periods, including only for patients entering add-on treatment set). For IA1 the plot was generated for patients with BOR of CR/PR/SD and for IA2 the plot will be generated for patients with BOR of CR/PR/SD/PD/NE (for BICR data, the category Non-CR/Non-PD will be added). Tumor response and overall response will be listed.

Sensitivity analysis

Additionally, sensitivity analysis based on confirmed CR/PR (RECIST 1.1) for BICR assessment for the CCI set will be performed.

Page 38 of 78 Version: Final v7.0 Date: 05Mar2024

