8.4.3.5 Analysis for Add-on Treatment Set

The analysis of endpoints ORR, DCR, DOR, TTR, PFS described in Sections 8.4.2.1, 8.4.2.2, 8.4.2.3, 8.4.2.4, 8.4.2.5 and 8.4.2.6 will be repeated for the Add-on Treatment set using the response for BICR and Investigator assessment based on the RECIST 1.1 and iRECIST guidelines. Per Section 8.1, these analyses will be based on data collected from the date of first dose of add-on treatment and after. For TTR and PFS, the starting date is the date of first dose of add-on treatment.

The analysis of DEoR for the add-on treatment set is in Section 8.4.3.4.

8.4.3.6 Overall Survival for arm 2 and arm 3

Analysis of OS will be performed for the BNT111 mono and cemiplimab mono treatment groups using the same method as Section 8.4.2.7 for the CCI set.

The analysis will be repeated for each of the following:

- Add-on treatment Set using the BNT111 + add-on cemiplimab and cemiplimab + add-on BNT111 treatment groups (the definition of overall survival will be the same as that in Section 8.4.2.7 e.g. starts from the date of randomization)
- The CCI set excluding patients that are in the Add-on Treatment set

Page 42 of 78 Version: Final v7.0 Date: 05Mar2024

An additional analysis would also be performed for the BNT111 + add-on cemiplimab and cemiplimab + add-on BNT111 treatment groups using the Add-on Treatment set. OS, for this analysis, would be defined as the time in months from date of first dose of add-on treatment to death from any cause.

Censoring rules are in appendix Table 5.2.

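### The SAP does not define the tumor baseline for add-on analyses when the add-on scan precedes AOC1D1, and its data cut does not exempt that scan

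*SAP*

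**What the plan says.** **Data cut.** SAP 8.1 covers ORR, DCR, DOR, DDC, TTR, depth of response and PFS with one rule: "For the analysis using the Add-on Treatment set, only the data from date of first dose of add-on treatment will be used". SAP 8.4.3.4 repeats this limit for depth of response in the Add-on Treatment set.

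**Baseline.** SAP 8.1 gives a general definition: "Baseline is defined as last non-missing value prior to the first dose of trial treatment at C1D1". It then adds, for the add-on period: "For the add-on treatment if the baseline visit and AOC1D1 are on the same day, the assessment only needs to be taken once". It continues: "In this case the AOC1D1 would be considered as the baseline value", unless the assessment followed dosing. There is no rule for a baseline visit before AOC1D1. If baseline or post-baseline is missing, change from baseline is set to missing.

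**Add-on scan.** Protocol 1.3.2 (SOA2, footnote m) says: "Baseline image may not be older than 21 d prior to AOC1D1". Target and non-target lesions can be redefined at that scan. SAP Appendix 4 (SOA2, footnote n) says the same.

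**Percent change.** SAP 8.4.3.4 computes percent change from baseline without saying which baseline applies to add-on patients. Appendix 7 has a Screening row and add-on rows from Week 6, but no add-on baseline row.

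**Stable disease.** SAP 8.4.1 notes that "a tumor response of SD can be confirmed from 36 days after first dose of study drug". SAP 8.4.2.2 (DCR) and 8.4.3.2 (DDC) count the 6 weeks (±1) from first dose. SAP 8.4.3.5, which repeats DCR for the Add-on Treatment set, does not say that this count restarts.

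**The concern.** Patients enter add-on therapy after centrally verified progression, so the C1D1 sum describes their disease before the event that qualified them. The sensible reference for activity during add-on is the scan taken just before the first add-on dose, with the lesions chosen there. The SAP never says so for the ordinary case in which that scan precedes AOC1D1.

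A programmer following the text has two literal routes, and neither gives a usable result. At stake is the exploratory objective on anti-tumor activity during add-on, chiefly the outputs the SAP computes from tumor sums: depth of response, waterfall and spider plots, and the reference point for tumor size by visit. Up to 90 patients could contribute (45 in each of Arms 2 and 3, SAP Table 3.2), although only those who progress and re-consent will do so.

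**Working it through.** The plan gives no figure to reproduce here. The check is a reading of the rules plus two small calculations.

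**1. Which add-on baseline scans survive the cut?** The permitted dates run from 21 days before AOC1D1 to AOC1D1 itself: 21 + 1 = 22 dates. A cut at the date of the first add-on dose keeps 1 of the 22. A scan on any of the other 21 falls in the randomized-period data, which SAP 8.1 runs up to the day before that dose.

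**2. What reference is left?**
- *Cut applied to every scan.* The earlier add-on scan is removed, and so is the C1D1 scan. Baseline is missing, so change from baseline is missing.
- *Baselines treated as outside the cut, general definition applied.* The reference is the C1D1 sum, possibly of lesions no longer followed.
- *Add-on baseline scan as reference.* This is presumably the intention, but it is written only for the same-day case.

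**3. Size if C1D1 is the reference.** Let g be growth in the sum from C1D1 to the add-on baseline and c the true change from the add-on baseline, in the same lesions. Then:

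shown change = (1 + g)(1 + c) - 1

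The values of g and c are assumptions. With c = -30%:

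| g | Calculation | Shown change |
|---|---|---|
| 10% | 1.10 × 0.70 - 1 | -23% |
| 20% | 1.20 × 0.70 - 1 | -16% |
| 30% | 1.30 × 0.70 - 1 | -9% |
| 50% | 1.50 × 0.70 - 1 | +5% |

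With the add-on baseline as reference, every row is -30%. Conversely, to show -30% from C1D1 the true reduction must be 1 - 0.70/1.20 = 41.7% at g = 20%, or 1 - 0.70/1.50 = 53.3% at g = 50%.

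**4. The SD minimum.** The first scheduled scan is 6 ± 1 weeks after treatment start, so no earlier than 5 × 7 = 35 days. Progression normally needs a second scan at least 4 weeks later: 35 + 28 = 63 days. Counted from the first dose of study drug, the 36-day minimum has therefore normally passed before add-on starts. Scheduled add-on scans are themselves 6 ± 1 weeks after add-on start, so they would largely meet a restarted minimum too. The difference is confined to SD read at an early unscheduled scan, and SAP 8.1 does include unscheduled assessments in tumor response analyses.

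**The case against.** The strongest reply is that the SAP plainly knows of an add-on baseline. Its schedule has an add-on baseline column with CT/MRI, repeats the 21-day limit and allows lesions to be redefined. The same-day sentence resets the baseline to AOC1D1. The footnote to the objectives table ties C1D1 to the main trial: "Baseline in the main trial (Arm 1) encompasses all data collected before start of trial therapy on Visit C1D1". Protocol 8.1.2 lets the scan that confirmed progression serve as the add-on baseline and requires the redefined lesions to be followed. In SAP 8.4.3.4 the date limits can be read as choosing the scans from which the maximum reduction is picked, not as defining the denominator. The Appendix 7 rows are labelled illustrative; they place Add-on Week 6 at day 43, which makes sense only if days run from the first add-on dose, so restarting the SD count is a natural reading too.

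Much of this stands. A reader might infer that the SAP ignores the add-on baseline, or that C1D1 is certainly the add-on reference. The documents support neither: the add-on baseline is recognized, and a fully literal cut removes C1D1 as well. What the reply does not supply is a sentence naming the tumor baseline for a scan before AOC1D1, or exempting that scan from the cut. SAP 8.4.3.4 also says the restricted data are those used to derive depth of response, so the selection-only reading is not secure.

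**Conclusion.** The gap is real and worth closing. As written, the rules leave add-on percent change either missing or referenced to a pre-progression sum; the correct reference is left to the programmer. The range of -16% to +5% for a true 30% reduction applies only to the second outcome and rests on assumed growth of 20 to 50% in the same lesions. SAP 10.8 allows progression on non-target or new lesions, so some patients' target sums may have grown less. The SD effect is likely small.

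Two wider inferences are not supported:
- *That add-on ORR, DOR and PFS are wrong in the same way.* These rest mainly on responses assigned by the central readers or investigators, who can already work from the add-on baseline.
- *That the time origin is wrongly reset for only two endpoints.* SAP 8.4.3.5 says: "For TTR and PFS, the starting date is the date of first dose of add-on treatment". DOR and DDC start at response or disease control, ORR and DCR have no time origin, and SAP 8.4.3.6 separately defines OS from the first add-on dose.

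All add-on efficacy analyses are exploratory. The primary Arm 1 ORR is unaffected.

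**What to change.** Change the SAP only:

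- **8.1:** for the Add-on Treatment set, define the tumor baseline as the last non-missing assessment made before the first add-on dose, and exempt it from the restriction to data from that dose onward.
- **8.4.3.4:** name that assessment as the reference for add-on percent change, in the summaries and in the waterfall and spider plots.
- **Appendix 7:** add an Add-on Baseline row running from 21 days before AOC1D1 to pre-dose on AOC1D1.
- **8.4.1, 8.4.2.2 and 8.4.3.2:** for Add-on Treatment set analyses, count the SD minimum from the first add-on dose.

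The cost is SAP wording and programming on scans already collected. Add-on DCR may fall slightly if early SD readings no longer count. The protocol's schedule of activities needs no change.

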- f "n" represents the number of the respective cycle (e.g., C4 means fourth cycle of treatment).
- g Visit CnD1 should occur 21 (± 3) d after the first day (i.e., treatment visit) of the previous cycle.
- h Informed consent must be documented before any trial-specific screening procedure is performed.
- i Eligibility should be confirmed and documented in the eCRF. This should be performed when all screening results are available and within 21 d after initiation of screening.
- j Underlying disease history should include histology, TNM stage at diagnosis (including which AJCC edition), prior anti-cancer therapies/procedures, date of last progression.
- k BRAF V600 mutation status may be obtained from medical history data.
- TNM staging at the time of trial entry to be performed according to AJCC 8th edition.
- m Concomitant medication and therapy includes any therapies (e.g., prescription drugs, over-the-counter drugs, vaccines, herbal or homeopathic remedies, nutritional supplements) used by a patient in addition to protocol-mandated trial treatment from 28 d prior to initiation of trial treatment until the SFU2 visit.
- n Vital signs (body temperature, pulse rate, respiratory rate, and blood pressure) should be measured within 60 min prior to the administration of the trial treatment(s) and at 30 (±10) min, 60 (±10) min, 4 h (±10 min), and 6 h (±10 min) after administration, or if clinically indicated (see Section 8.2.3 for guidelines on reduction or expansion of these time points).
- o At screening and at EoT assessments must include a full physical examination. Record abnormalities observed on the respective eCRF pages as appropriate. For all subsequent physical examinations perform a limited, symptom-directed examination at specified time points and as clinically indicated at other time points. Record new or worsened clinically significant abnormalities on the AE eCRF.
- p Single 12-lead ECG recordings will be obtained during screening, at EoT, and as clinically indicated at other time points. Patients should be resting in a supine position for ≥ 10 min prior to ECG recording. The interpretation of the ECG recording will be done locally by the investigator.

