Additionally, the occurrence of abnormal vital sign results within a patient will be analyzed using descriptive summary statistics for each parameter and visit by treatment group.

ECG

ECG parameters and the scheduled time points for assessment are presented in Section 8.2.4 and Section 1.3.

Page 96 of 133 Version: 7.0 Date: 09 FEB 2023

ECGs will be judged by the investigator as clinically significant (yes/no). The number and percentage of patients with clinically significant ECG findings will be summarized by treatment group for each visit.

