8 STATISTICAL ANALYSES

8.1 General considerations

In general, the statistical analysis of efficacy will be performed by treatment group. Exploratory analysis will be performed for patients in the calibrator arms who went on to receive add-on treatment.

No formal statistical comparisons between treatment groups will be performed.

Continuous variables will be summarized by treatment group and total (as specified) using the following descriptive statistics: number of patients with non-missing data (n), mean, standard deviation (SD), median, minimum (min) and maximum (max).

Categorical variables will be summarized by treatment group and total (as specified), presenting absolute and relative frequencies (n and %) of patients in each category and the number of patients with missing data (missing' category will be presented if there is one or more missing value). The "(N=xx)" in the tables denotes the number of patients in the

Statistical Analysis Plan (SAP) BNT111-01

Page 28 of 78 Version: Final v7.0 Date: 05Mar2024

analysis set within each treatment group. For event-driven occurrence data (e.g., adverse event, concomitant medication, etc.) the percentages will be based on the number of patients in the analysis set (N). For reported visit data (e.g., gender, ECOG, etc.) the percentages will be based on the number of patients with non-missing values (n).

The rates of binary endpoints will be summarized by treatment group with absolute and relative frequencies (n and %) along with two-sided 95%-confidence intervals (CI) using an exact method. Exact confidence intervals for binomial proportions will be derived using the Clopper-Pearson method (Clopper, CJ and Pearson, ES⁵).

Time-to-event-endpoints will be analyzed using Kaplan-Meier methodology by treatment group and censored in accordance with the FDA Guidance: "Clinical Trial Endpoints for the Approval of Non-Cell Lung Cancer Drugs and Biologics² (Table 5.1). The main analysis will be done for each treatment group separately. Comparison of the treatment groups may be done as an exploratory analysis, with stratified and non-stratified analysis considered.

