All trial data will be presented at the visit as collected in the eCRF. No windowing of data for the purposes of assigning to a visit will occur.

Statistical Analysis Plan (SAP) BNT111-01

Page 31 of 78 Version: Final v7.0 Date: 05Mar2024

Unscheduled assessments will be included in the analysis of efficacy endpoints for tumor response, time to event endpoints and shift from baseline to worst NCI-CTCAE Grade laboratory summary tables. All other unscheduled assessments will be listed only and not included in summaries/analysis.

If there is a difference between randomized and actual strata at randomization then the randomized strata will be used for analyses. A summary of randomized and actual strata at randomization will be presented. If there is a notable difference between the two summaries, then a sensitivity analysis for the primary endpoint will be considered.

Handling missing Data:

For the purposes of assigning treatment-emergent flag for AEs, partial or missing AE dates will be handled as follows:

- If the day of the month is missing, the onset day will be set to the first day of the
 month unless it is the same month and year as the first trial treatment. In this case,
 in order to conservatively report the event as treatment-emergent, the onset date will
 be assumed to be the date of the first trial treatment.
- If the onset day and month are both missing, the day and month will be assumed to be January 1, unless the event occurred in the same year as the first trial treatment.
 In this case, the event onset will be assumed to be the day and month of treatment in order to conservatively report the event as treatment-emergent.
- A completely missing onset date will be assumed to be the day of the first trial treatment.
- If an AE has a partial start date that is in the same month/year as the first dose of trial treatment, then the AE will be reported as treatment-emergent. If an AE has a missing start date, then the AE will be reported as treatment-emergent.

For the purposes of assigning treatment-emergent flag for irAEs, partial or missing irAE dates will be handled as follows:

- If the day of the month is missing, the onset day will be set to the first day of the
 month unless it is the same month and year as the first trial treatment of cemiplimab.
 In this case, in order to conservatively report the event as treatment-emergent, the
 onset date will be assumed to be the date of the first trial treatment of cemiplimab.

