8.5.5 ECG

ECG parameters to be summarized include QT, QTcF, PR, and QRS intervals in msec, heart rate (bpm).

ECG parameters will be summarized by presenting summary statistics of the observed and change from baseline values by visit and treatment group.

Investigator interpretation of ECGs will be summarized as for categorical data by treatment group for each visit.

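### The ECG summaries may contain no on-treatment recordings; one worst post-baseline table would close the gap at almost no cost

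*SAP*

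**What the plan says.** **Schedule.** Protocol Section 1.3.1, footnote p, for the randomized period: "Single 12-lead ECG recordings will be obtained during screening, at EoT, and as clinically indicated at other time points". Section 1.3.2, footnote l, for the add-on period: "Single 12-lead ECG recordings will be obtained during baseline, at EoT, and as clinically indicated at other time points". In both schedules the ECG row across the treatment cycles carries only an if-indicated entry.

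**Unscheduled values.** SAP 8.1 brings unscheduled assessments into the tumor response analyses and into "time to event endpoints and shift from baseline to worst NCI-CTCAE Grade laboratory summary tables". For everything else: "All other unscheduled assessments will be listed only and not included in summaries/analysis". ECG is not named as an exception.

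**Visit labels.** SAP 8.1: "All trial data will be presented at the visit as collected in the eCRF". No windowing is applied to assign data to visits. Where a visit or day has several post-baseline values, the first is used.

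**Planned ECG output.** Protocol 9.4.5: "The number and percentage of patients with clinically significant ECG findings will be summarized by treatment group for each visit". SAP 8.5.5 summarizes QT, QTcF, PR, QRS and heart rate as observed values and change from baseline by visit, and adds: "Investigator interpretation of ECGs will be summarized as for categorical data by treatment group for each visit". Neither document has a worst-value or any-time post-baseline ECG table.

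**The concern.** An ECG taken for a clinical reason during treatment is plausibly more informative about cardiac safety than a routine one before or after treatment. Protocol Table 3 lists myocarditis and pericarditis among the immune-related reactions to be managed, and Section 6.8.4.1 describes tachycardia and moderate to severe hypotension with BNT111. If the summary rules drop the indicated recordings, or scatter them over visits with very few patients at each, a reader of the ECG tables sees little of what happened while patients were being dosed. A QTcF, PR or QRS change that resolved before EoT would leave no trace in the tables meant to describe those intervals.

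**Working it through.** No power, alpha or sample-size figure is involved and the plan states no number to reproduce. The check applies the SAP rules to the ECG schedule.

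1. **Count the fixed ECG time points** (protocol Sections 1.3.1 and 1.3.2).
   - Randomized period: screening and EoT. Fixed during treatment cycles: 0. Fixed post-baseline: 1 (EoT).
   - Add-on period: add-on baseline and EoT. Fixed during treatment cycles: 0. Fixed post-baseline: 1 (EoT).
   - EoT falls 0 to 21 days after the last dose and takes place only after both drugs have stopped.
   - The ECG footnotes in the SAP's own schedules omit EoT, but the SAP table rows still mark it, so the count is the same.

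2. **Reading A: indicated ECGs are recorded as unscheduled.** They match none of the three exceptions in SAP 8.1, so they are listed only. The by-visit ECG tables then hold baseline and EoT and no on-treatment recording. This is the natural reading: protocol 9.4.5 refers to Section 1.3 for the scheduled ECG time points, and Section 1.3 places indicated ECGs at other times.

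3. **Reading B: indicated ECGs are recorded under a cycle visit.** They appear at that visit. For visit data, SAP 8.1 takes percentages over patients with a non-missing value, so the denominator is the patients who had an ECG for cause at that visit. If a patient had several that day, the first counts, even if a later one is worse. Patient counts cannot be added across visits to give a treatment-period count, because one patient may appear at several.

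4. **Arms 2 and 3 with add-on.** These patients have no EoT visit before add-on starts, and SAP 8.1 cuts Safety-set data (other than adverse events) at the day before the first add-on dose. Their only fixed post-baseline ECG under monotherapy is the add-on baseline recording. If it is taken on the first add-on day, that cut-off excludes it too.

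5. **Compare with laboratory data.** SAP 8.1 admits unscheduled values to the laboratory worst-grade shift tables, although hematology and chemistry are also drawn at every treatment visit. ECG has no fixed on-treatment recording, so a worst-value summary depends entirely on the indicated ones.

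Under neither reading do the ECG tables give a per-patient summary of ECG findings during treatment.

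**The case against.** The strongest reply is that the adverse event tables already carry the important information. Protocol 8.2.4 obliges the investigator to review each ECG and enter clinically relevant changes as adverse events, and Section 10.3.1.1 makes a clinically significant ECG abnormality an adverse event. SAP 8.5.2 tabulates treatment-emergent events by term and worst grade, with the analysis-set N as denominator under SAP 8.1. Myocarditis and pericarditis are on the protocol's immune-related event list, and cemiplimab-related immune events of Grade 3 or higher are tabulated as events of special interest. Blood pressure and heart rate have their own summaries by visit and post-dose time point (SAP 8.5.4). All safety data are listed (SAP 8.5). This stands, and it confines the point to the ECG summaries. It does not remove it, because adverse event tables do not show QTcF, PR or QRS values or their change from baseline.

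It can also be said that both documents plan ECG summaries by visit and the SAP delivers them. That stands too. A reader might infer that the planned percentage of patients with clinically significant ECG findings is wrong for the treatment period. The documents do not support this: neither promises a treatment-period ECG percentage, and ECG is not among the safety endpoints in protocol Section 3. Nor is a percentage over the patients actually assessed an error, since that is the SAP's stated denominator rule. It is only hard to interpret when patients are tested for cause.

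Finally, that indicated ECGs count as unscheduled is an inference. For coagulation, which has a similar schedule, the protocol mentions if-indicated tests and unscheduled tests separately, and the eCRF is not available. This is why both readings are worked through.

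**Conclusion.** A minor improvement to reporting. On the natural reading the ECG tables contain baseline and EoT only; on the other reading they contain thin, first-value-only rows for patients tested for cause. Either way the summaries are less informative than the collected data allow, most clearly for QTcF, PR and QRS.

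No numerical size can be given: the documents do not say how many indicated ECGs are expected or how often they are abnormal. A reader might infer that on-treatment cardiac findings are lost to the report. They are not, given the adverse event recording and the listings. The primary endpoint is unaffected. The conclusion rests on the SAP text as it stands; which of the two readings applies depends on how the eCRF labels indicated ECGs.

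**What to change.** In SAP 8.5.5, add a per-patient summary over all post-baseline ECGs, scheduled or not, within each treatment period as already delimited in SAP 8.1:

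- worst post-baseline investigator interpretation;
- worst post-baseline change from baseline in QTcF, PR and QRS, with the direction of worst stated.

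Show both the number of patients with at least one post-baseline ECG and the Safety-set N (the Add-on Treatment set N for the add-on period). The first shows how many patients the finding rests on; the second avoids presenting a tested-for-cause group as the whole arm.

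Name this table in the SAP 8.1 exception list. Adding ECG to that list alone would not be enough, because an unscheduled ECG has no place in a by-visit table when no windowing is allowed. A sentence on how the eCRF labels indicated ECGs would settle which reading applies.

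Cost: a few SAP sentences and one table per period, from data already collected. The ECG schedule and clinical conduct do not change.
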